16.1. ADVERSE EVENTS

Adverse Events (AEs) will be coded using MedDRA central coding dictionary, Version 19.1 or higher. The SOC's will be sorted by internationally agreed EMA SOC order (refer to APPENDIX 3); PTs will be sorted by decreasing frequencies (within system organ class).

A summary of the number of subjects and percentages within each of the categories described in the sub-section below will be provided.

In case of worsening in intensity, a new entry is created with start date equal to start of worsening.

Listings will include Treatment-Emergent Adverse Events (TEAEs) and Non-TEAEs.

Document:	\\ieedc-vnasc01\BIOSdata\Boehringer_Ingelheim\BI_695501\NVA96252\Biostatistics\Documentation\SAP\BI1297.4 SAP FINAL v4.0_22MAY2019.docx		
Author:	Version Number:	Final V4.0	
	Version Date:	22MAY2019	
Template No:	CS_TP_BS016	Revision 5	Reference: CS_WI_BS005
Effective Date:	01Apr2018		

16.1.1. ADVERSE EVENT SPECIFIC DERIVATION

16.1.1.1. Treatment Emergent Adverse Event

Treatment-Emergent Adverse Events (TEAEs) are defined as AEs that started or worsened on or after the first dose of trial medication and prior to the last date of trial medication + 10 weeks (70 days) inclusive.

There are two specific periods of interest:

Period 1 Treatment-Emergent Adverse Events (P1 TEAEs) are defined as AEs that started or worsened on or after the first dose of trial medication and prior to the date of Week 24 visit or within 10 weeks (70 days, inclusive) after the last dose of IMP for patients who discontinued the treatment before Week 24.

Period 2 Treatment-Emergent Adverse Events (P2 TEAEs) are defined as AEs that started or worsened on Week 24 visit and prior to or on the Week 56 visit or within 10 weeks (70 days, inclusive) after the last dose of IMP for patients discontinuing treatment prior to Week 46.

Non-TEAEs will be classified as "Screening" if AE start date is strictly prior to the first injection date. Non-TEAEs will be classified as "Post treatment" if AE start date is strictly after the last injection date + 70 days.

See APPENDIX 2 for handling of partial dates for AEs. In the case where it is not possible to define an AE as treatment-emergent or not, the AE will be classified by the worst case, i.e., treatment-emergent in the period of the last injection of trial medication.

16.1.1.2. Risk ratio

Risk ratios and associated 95% exact confidence interval will be presented for all adverse events.

Risk ratio will be defined as: $[a/(a+b)]/[c/(c+d)]$

where:

- **a** is the number of subjects with AE within treatment group BI 695501
- **a+b** is the total number of subjects in treatment group BI 695501
- **c** is the number of subjects with AE within treatment Humira
- **c+d** is the total number of subjects in treatment group Humira

PROC FREQ with option RELRISK will be used for programming purpose.

```
proc freq data=data;  
  tables trt*ae_overall;  
  exact relrisk(method=score);  
  weight count;
```

run;

Document: \\ieedc-
vnasc01\BIOSdata\Boehringer_Ingelheim\BI_695501\NVA96252\Biostatistics\Documentation\S
AP\BI1297.4 SAP FINAL v4.0_22MAY2019.docx

Author: Version Number: Final V4.0
Version Date: 22MAY2019

Template No: CS_TP_BS016 Revision 5
Effective Date: 01Apr2018

Reference: CS_WI_BS005

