4.1.4 Drug assignment and administration of doses for each patient

Each patient will receive 160 mg (loading dose) of BI 695501 or EU-approved Humira at the Baseline Visit (Day 1) followed by 80 mg of BI 695501 or EU-approved Humira 2 weeks later (Day 15/Week 2), and then 40 mg of BI 695501 or EU-approved Humira at Week 4 (primary endpoint).

At Week 4 (Day 29), patients achieving a clinical response (defined as a decrease in CDAI \geq 70) will continue receiving their randomized treatment (40 mg BI 695501 or EU-approved Humira every 2 weeks) in a blinded fashion. The hematocrit value required to determine CDAI score at Week 4 will be assessed locally and confirmed via central laboratory

Boehringer Ingelheim		12 Dec 2017
BI Trial No.: 1297.4		
c09542349-05	Trial Protocol	Page 34 of 93

assessment. At Week 24, patients originally randomized to EU-approved Humira will switch to receive 40 mg BI 695501 every 2 weeks. All patients will then continue to receive BI 695501 at the same dose until Week 46.

Patients not achieving a clinical response at Week 4 will not receive any further treatment with trial medication, but will be followed up for safety after 10 weeks (Safety Follow-up Visit).

Prefilled syringes will be used for the administration (see Section 4.1.1) and all patients will receive their injections at the trial site throughout the trial until Week 22, and BI 695501/EU-approved Humira will be administered by a dedicated, unblinded member of trial personnel (third party blinding). From Week 24 onwards, when all patients will be receiving BI 695501when all patients will be receiving BI 695501, any suitably trained trial personnel may administer the medication to the patient. However, patients and other trial personnel must remain blinded with respect to the initial assignment to EU-approved Humira or BI 695501.

After the first injection in the induction period (Visit 2) and the injection at Visit 14 (when patients originally randomized to EU-approved Humira will switch to receive BI 695501), patients will remain at the clinical site for at least 1 hour for observation of any AEs.

Dose modification is not permitted during this trial. If a patient misses a dose of trial medication then the dose should be administered as soon as possible, in accordance with the visit schedule presented in Flow Chart A and Flow Chart B.

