7.3.4 Safety analyses

Adverse events will be coded using the MedDRA coding dictionary.

Boehringer Ingelheim		12 Dec 2017
BI Trial No.: 1297.4		
c09542349-05	Trial Protocol	Page 65 of 93

All treated patients will be included in the safety analysis. In general, safety analyses will be descriptive in nature. No hypothesis testing is planned. No formal inferential analyses are planned for safety comparison. The analyses will be based on the SAF.

Statistical analysis and reporting of AEs will concentrate on treatment-emergent AEs. To this end, all AEs occurring between start of treatment and end of the REP will be considered 'treatment-emergent'. The REP is defined as 10 weeks after the last dose of trial medication. Adverse events that start before first drug intake and deteriorate under treatment will also be considered as 'treatment-emergent'. Other AEs will be assigned to the appropriate trial phases, i.e., screening or post-treatment. For patients switching from EU-approved Humira to BI 695501, AEs occurring after the first dose of BI 695501 will be assigned to BI 695501 for the overall AE analysis. AEs occurring before the first dose of BI 695501 will be assigned to the ongoing treatment.

Frequency, severity, and causal relationship of AEs will be tabulated by system organ class and preferred term after coding according to the current version of MedDRA. In addition, RR and risk difference together with 95% CIs will be presented for the overall population (details will be specified in the TSAP).

Laboratory data will be analyzed quantitatively as well as qualitatively. The latter will be done via comparison of laboratory data with their reference ranges. Values outside the reference range as well as values defined as clinically relevant will be highlighted in the listings. Treatment groups will be compared descriptively with regard to distribution parameters as well as with regard to frequency and percentage of patients with abnormal values or clinically relevant abnormal values.

Vital signs, physical examinations, or other safety-relevant data observed at screening, baseline, during the course of the trial and at the end-of-trial evaluation will be assessed with regard to possible changes compared with findings before start of treatment.

Page 66 of 93

Proprietary confidential information © 2017 Boehringer Ingelheim International GmbH or one or more of its affiliated companies

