13.1. DERIVATIONS

The date of first and last trial medication administration will be taken from the eCRF page "Trial Medication Injection".

Duration of exposure (days) = (date of last injection - date of first injection + 1).

Duration of exposure (weeks) = Duration of exposure (days)/7.

Patient Year Exposure (year) = cumulative duration of exposure in days per subject/365.25.

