16. SAFETY OUTCOMES

All outputs for safety outcomes will be based on the SAF for overall and Period output.

There will be no statistical comparisons between the treatment groups for safety data, unless otherwise specified with the relevant section.

Safety will be assessed as a secondary objective in this trial.

The safety endpoints considered as secondary endpoints are defined as:

- Proportion of patients with AEs, SAEs, and AESIs (e.g., serious infections)
- Proportion of patients with infections/serious infections (seriousness of infection defined as requirement of i.v. antibiotics for treatment and/or meeting seriousness criteria to be qualified as an SAE)
- Proportion of patients who experience hypersensitivity reactions
- Proportion of patients who experience DILI (Drug Induced Liver Injury)
- Proportion of patients with injection-site reactions

Another safety endpoint is the proportion of patients who discontinue due to drug-related AEs and AESIs (e.g., serious infections and allergic reactions).

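### AE risk ratios and differences use crude patient counts although Week 4 response sets time at risk, so unequal response between arms can distort the safety comparison

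*SAP*

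**What the plan says.** - **Measure.** SAP 16.1.1.2: "Risk ratios and associated 95% exact confidence interval will be presented for all adverse events". The ratio is the share of patients with an AE on BI 695501 divided by the share on Humira, and the first denominator "is the total number of subjects in treatment group BI 695501". SAP 16.1.1.3 takes the risk difference from the same code.
- **Scope.** The code line is "tables trt*ae_overall". Protocol 7.3.4 says that "RR and risk difference together with 95% CIs will be presented for the overall population". SAP 16 says that "All outputs for safety outcomes will be based on the SAF for overall and Period output". No sentence states whether risk ratios and differences are produced for Period 1.
- **AE window.** SAP 16.1.1.1 ends Period 1 at the Week 24 visit, or "within 10 weeks (70 days, inclusive) after the last dose of IMP for patients who discontinued the treatment before Week 24".
- **Who stops.** Protocol 4.1.4: "Patients not achieving a clinical response at Week 4 will not receive any further treatment with trial medication". Flow Chart A places the safety follow-up visit of these patients at Week 14, Day 99.
- **Switch.** Humira patients move to BI 695501 at Week 24. Protocol 7.3.4 assigns their later AEs to BI 695501 in the overall analysis.
- **Person-time.** SAP 13.1: "Patient Year Exposure (year) = cumulative duration of exposure in days per subject/365.25", where duration runs from first to last injection. It serves the exposure tables. The available text describes no exposure-adjusted AE rate and no time-to-event AE analysis.

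**The concern.** A crude proportion compares arms fairly when patients are at risk for similar lengths of time. Here a post-randomisation efficacy result decides how long a patient is counted, so an arm with fewer Week 4 responders accumulates less AE observation. Its crude AE proportion then falls even when the underlying AE rate is the same.

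Comparing safety across induction and maintenance is a secondary objective. Period 1 is the longest randomised safety comparison before the Humira arm switches. The overall table, which is the one the SAS line names, has a larger gap in follow-up and also carries the reassignment of AEs after the switch. A small apparent safety advantage in either table could be read as a product property when it partly reflects earlier stopping.

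**Working it through.** **1. Reproduce the plan's follow-up day.** Last dose on Day 29: 29 + 70 = Day 99, as in Flow Chart A. Last dose on Day 15: 15 + 70 = Day 85. Protocol 4.1.4 supports both readings: it gives every patient a Week 4 dose, and it also says that non-responders receive nothing further. Both are carried through.

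**2. Share of Period 1.** The Week 24 visit is Day 169, so Period 1 has 168 days. 85/168 = 51%; 99/168 = 59%.

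**3. Inputs.**
- Response rates: 85% vs 75%, the widest gap in Protocol Table 7.7: 1; and 80% vs 0.76 × 80% = 60.8%, from the planning rate and the margin in Protocol 7.3.1.
- Patients: 65 per arm (Protocol 7.7).
- Assumptions, because the documents give no AE incidence: the same constant hazard in both arms, all early stops at Week 4, and a 24-week risk P of 30% (range 5% to 70%).

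**4. Mean weeks at risk** = 24r + T(1 − r), with r the response rate and T = 12 or 14 weeks.
- 85% vs 75%, T = 12: 22.2 and 21.0, ratio 0.946. T = 14: 22.5 and 21.5, ratio 0.956.
- 80% vs 60.8%, T = 12: 21.6 and 19.3, ratio 0.893. T = 14: 22.0 and 20.08, ratio 0.913.

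**5. Expected crude risk per arm** = rP + (1 − r)[1 − (1 − P)^(T/24)]. For P = 0.30 the bracket is 1 − 0.7^0.5 = 0.163 (T = 12) or 1 − 0.7^0.583 = 0.188 (T = 14).

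| Humira vs BI response | T (weeks) | Humira risk | BI risk | Crude RR |
|---|---|---|---|---|
| 80% vs 80% | 12 or 14 | equal | equal | 1.00 |
| 85% vs 75% | 12 | 28.0% | 26.6% | 0.951 |
| 85% vs 75% | 14 | 28.3% | 27.2% | 0.960 |
| 80% vs 60.8% | 12 | 27.3% | 24.6% | 0.904 |
| 80% vs 60.8% | 14 | 27.8% | 25.6% | 0.922 |

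Over P from 5% to 70%, the RR is 0.947-0.971 at 85% vs 75% (risk difference −0.2 to −2.5 points) and 0.895-0.943 at the margin (−0.4 to −4.8 points). Person-time denominators give an expected 1.00 throughout under the same assumptions.

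**6. Direction.** Let non-responders have k times the responders' AE rate after Week 4. The bias cancels when 4 + k(T − 4) = 24, that is k = 20/(T − 4): 2.5 for T = 12 and 2.0 for T = 14. Above that it reverses; at k = 4 and 85% vs 75%, the RR is 1.03-1.07.

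**7. Sampling error.** At 85% vs 75%, P = 50% and T = 12, the risks are 46.9% and 44.8%, RR 0.956. SE(log RR) = √[0.531/(0.469 × 65) + 0.552/(0.448 × 65)] = 0.19. The approximate 95% CI is 0.66-1.39, and the bias is about 0.24 SE.

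**8. Overall table, 56 weeks, before any reassignment at the switch.** Non-responders have 85/392 = 22% or 99/392 = 25% of full follow-up. With the hazard of step 5, the 56-week risk is 1 − 0.7^(56/24) = 56.5%. At 85% vs 75% and T = 12, BI is 0.75 × 0.565 + 0.25 × 0.163 = 46.5% and Humira is 0.85 × 0.565 + 0.15 × 0.163 = 50.5%, RR 0.92. Over 24-week risks of 10% to 50% and both T, the RR is 0.91-0.94.

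**The case against.** The strongest reply is that the endpoint is the proportion of patients with AEs, safety is descriptive in an exploratory trial, and no decision rests on these ratios. That stands: the crude proportion is the defined endpoint and should stay. Descriptive ratios will still be read as comparisons of the products, so the reader needs a version that separates rate from follow-up.

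The direction is conditional. The plan expects 80% response in both arms, which gives no bias. Worsening of the underlying disease counts as an AE (Protocol 5.3.6.2), and non-responders are off trial drug, so equal hazards are least secure in this group. A reader might infer that the less effective product will look safer; the documents support only that it can.

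A reader might also take Period 1 as the only randomised safety comparison. It is not: the Week 4 primary analysis (SAP 4.1) reports safety by arm before responders and non-responders separate. Nor is it established that risk ratios are produced for Period 1. The code and Protocol 7.3.4 point to the overall table; SAP 16 makes a period version possible without specifying it.

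Rates have their own weakness. Treatment starts with the largest doses, so AEs may cluster early. For a rare AE occurring wholly before Day 85 at equal risk, the crude RR is correctly 1.00, while a rate ratio would be about 1/0.946 = 1.06 at 85% vs 75% and 1/0.893 = 1.12 at the margin. This stands, and is why a time-to-first-event estimate is needed too.

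Finally, SAP 9, 13 and 16.1.8 tabulate Week 4 responders, early stops, exposure time, and AEs after the last injection in patients stopped for lack of efficacy. These would reveal an imbalance but do not correct the comparison. The table templates are not in the available text.

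**Conclusion.** The concern holds in a limited form. AE comparisons rest on crude proportions, although the Week 4 efficacy result sets time at risk and leaves non-responders with 51-59% of Period 1. Under equal constant hazards, the expected distortion in the risk ratio is about 3-5% at the widest planned response gap and about 8-10% at the 0.76 margin for a 30% 24-week risk. It is larger in the overall table (RR 0.91-0.94 at 85% vs 75%).

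The Period 1 effect is zero with equal response and reverses once non-responders' AE rate after Week 4 exceeds about 2-2.5 times that of responders. At 65 per arm it is well inside sampling error. AE incidence and the rate multiplier are assumptions, and the overall figures ignore reassignment at the switch. This is a worthwhile, inexpensive improvement to the SAP, not a defect that invalidates the safety analysis.

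**What to change.** In SAP 16.1.1:

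1. State which periods receive the risk ratio and risk difference.
2. For TEAEs, SAEs, AESIs and infections, in Period 1 and overall, add patients with a first event per 100 patient-years at risk, with the rate ratio and 95% CI, beside the crude figures. Split overall time at the Week 24 switch.
3. Define time at risk as first dose to first event or to the end of the patient's own window in SAP 16.1.1.1. The patient-year variable in SAP 13.1 cannot be reused unchanged, because it stops at the last injection and omits the 70 days in which AEs still count.
4. For Period 1, add a time-to-first-event estimate (Kaplan-Meier risk or hazard ratio), because AEs may cluster early.
5. Reconcile the passages that leave a non-responder's last dose at Day 15 or Day 29, so that the window is defined.

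The cost is some extra table columns and one time-to-event output. No new data are needed, and the prespecified crude proportions remain. The rates rest on a roughly constant hazard. The Kaplan-Meier estimate beyond the day on which non-responders' windows close rests on the patients still under observation; both limits should be footnoted.

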16.1.1.3. Risk difference

The risk difference between both treatment groups will be displayed together with its 95% confidence interval (CI) using the same SAS code as in section 16.1.1.2.

16.1.2. ALL TEAEs

Number of subjects, percentages, and number of events overall and for period 1 and period 2 will be presented by SOC and PT and also broken down further by maximum intensity and relationship to trial medication.

Periods for TEAE's:

Period 1	Visit date within 
 • [first injection date; Week 24 Visit] or • [first injection date; last injection date + 10 weeks (70 days)] (for patients that discontinued the treatment before week 24)].
Period 2	Visit date within 
 • [Week 24 Visit; Week 56 Visit[or • [Week 24 visit; last injection date + 10 weeks (70 days)] (for patients that discontinued the treatment before week 56)].

16.1.2.1. Intensity

Intensity is classed as mild/ moderate/ severe (increasing intensity). TEAEs starting after the first dose of trial medication with a missing intensity will be classified as severe. If a subject reports a TEAE more than once within that SOC/ PT, the AE with the worst case intensity will be used in the corresponding intensity summaries.

16.1.2.2. Relationship to Trial Medication

A related AE is defined as a TEAE with the item "Causal Relationship between the event and the trial drug" ticked "Related" on the AE form of the eCRF according to the investigator.

TEAEs with a missing relationship to trial medication will be regarded as related to trial medication. If a subject reports the same TEAE more than once for the given period within that SOC/ PT and at least 1 episode was assessed as related, the TEAE will be regarded as related in the corresponding relationship summaries.

All drug related AEs will be listed.

In addition, the number and percentages of subjects who discontinue due to drug-related TEAEs will be prepared

Document: \\ieedc-vnasc01\BIOSdata\Boehringer_Ingelheim\BI_695501\NVA96252\Biostatistics\Documentation\SAP\BI1297.4 SAP FINAL v4.0_22MAY2019.docx

Author: Version Number: Final V4.0
Version Date: 22MAY2019

Template No: CS_TP_BS016 Revision 5
Effective Date: 01Apr2018

Reference: CS_WI_BS005

overall by SOC and PT.

16.1.3. TEAEs LEADING TO DISCONTINUATION OF TRIAL MEDICATION

TEAEs leading to permanent discontinuation of trial medication will be identified by using the “Action taken with trial drug due to AE” equal to “Drug Withdrawn” from AEs eCRF pages.

The number and percentages of subjects with TEAEs leading to permanent discontinuation of trial medication will be prepared overall and for period by SOC and PT.

The AEs causing treatment modification or drug withdrawal will be listed.

16.1.4. SERIOUS ADVERSE EVENTS

Serious adverse events (SAEs) are those events recorded as “Serious” on the Adverse Events page of the eCRF. A summary of serious TEAEs by SOC and PT will be prepared overall and for period including the number of subjects, percentages and number of events.

A summary of related SAEs by SOC and PT will also be prepared overall and for period.

The SAEs and Non-SAEs will be listed.

16.1.5. NON-SERIOUS ADVERSE EVENTS

Non-Serious TEAEs with incidence in preferred terms strictly greater than 5% in at least one of treatment groups by SOC and PT will also be displayed overall and for period.

16.1.6. ADVERSE EVENTS LEADING TO DEATH

TEAEs leading to Death are those events which are recorded as “Fatal” on the Adverse Events page of the eCRF. A summary of TEAEs leading to death by SOC and PT will be prepared overall including the number of subjects, percentages and number of events.

16.1.7. OTHER SAFETY ENDPOINTS AND ADVERSE EVENTS OF SPECIAL INTEREST

A summary of the number of subjects, percentages, and number of events within each of the categories described in the sub-section below will be provided by SOC and PT.

Document:	\\ieedc-vnasc01\BIOSdata\Boehringer_Ingelheim\BI_695501\NVA96252\Biostatistics\Documentation\SAP\BI1297.4 SAP FINAL v4.0_22MAY2019.docx		
Author:	Version Number:	Final V4.0	
	Version Date:	22MAY2019	
Template No:	CS_TP_BS016	Revision	5
Effective Date:	01Apr2018		Reference: CS_WI_BS005

In addition, the number and percentages of subjects who discontinue due to drug-related AESI (as reported by investigators and CTP specified) will be prepared overall by SOC and PT.

The below table describes the allocation of adverse events to AESI group and Other safety endpoints group:

Adverse Event :	AESI	Other safety endpoint
Serious infections	√	√
Infections		√
Hypersensitivity reactions	√	√
Drug induced liver injury	√	√
Injection site reactions		√
Anaphylactic reactions	√	√

16.1.7.1. Reported by Investigator

AESI reported by Investigators are those events recorded as “Adverse Event of Special Interest” equal to “Yes” on the Adverse Events page of the eCRF.

AESI reported by investigators and CTP specified are detailed in the following sections.

16.1.7.2. Infections and Serious Infections

Infections are those events with a SOC equal to “Infections and infestations”.

Serious infections are:

- AEs which are both infections and SAEs as reported on the Adverse Events page of the eCRF.
- AEs which are both infections and identified by the medical advisor as requiring class IV (intravenous) antibiotics.

Serious infection events of special interest (Serious infection AESI) are those events both identified as serious infection adverse events and recorded as “Adverse Event of Special Interest” equal to “Yes” on the Adverse Events page of the eCRF.

Infections and Serious Infections will be summarized. Infections / Serious Infections will also be listed. The listing will include the “Adverse Event of Special Interest” equal to “Yes” information from the Adverse Events page of

Document: \\ieedc-vnasc01\BIOSdata\Boehringer_Ingelheim\BI_695501\NVA96252\Biostatistics\Documentation\SAP\BI1297.4 SAP FINAL v4.0_22MAY2019.docx

Author: Version Number: Final V4.0
Version Date: 22MAY2019

Template No: CS_TP_BS016 Revision 5
Effective Date: 01Apr2018

Reference: CS_WI_BS005

the eCRF as a flag.

